3.3 Proposed activities

Artemether-lumefantrine prophylaxis trial

The study of AL versus a multivitamin will be a two-arm randomised open label comparative study. Laboratory assessments of malaria infection at baseline and day 28 post forest will be performed blind to treatment allocation and incidence of clinical cases during follow-up will be recorded.

Activities/outcomes

The main activity proposed is an *in vivo* clinical assessment of prophylaxis to prevent malaria in 4400 participant episodes in 50 villages in Stung Treng and Pursat Provinces, Cambodia. The subjects will be randomized in a one-to-one ratio between the ACT AL and a multivitamin preparation with no antimalarial activity.

The study sites have been chosen based on current information on incidence of malaria, known predominance of malaria among forest goers, presence of an established clinical research programme and feasibility to perform the proposed research activities.

Efficacy of AL ACT will be assessed through follow up visits 28 days (+/-7 days) after returning from the forest upon completing each course of prophylaxis when temperature, symptom questionnaires, brief physical examinations, and malaria parasite PCR, and, in selected individuals, parasite genetics will be performed. Episodes of confirmed clinical malaria among study participants at any time point between enrolment and follow-up will also be recorded.

All the organisations in this collaboration will work closely with local counterparts including the National Malaria Control Programmes (NMCPs), non-governmental and other relevant organisations. Training is an integral part of this collaborative working relationship, and the building of local research capacity is an essential component of all research plans.

All research-related activities, from study design, planning, implementation through to analysis and writing of reports will be performed jointly with local counterparts. Both on-the-job training and formal training will be provided when needed, in particular for Good Clinical Practice (GCP) skills.

The close interaction between WHO and its regional offices will ensure that new knowledge is disseminated efficiently and effectively throughout the region.

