5. TRIAL DESIGN

5.1 Study sites

The study will take place at up to 50 villages in selected malaria endemic districts in Stung Treng and Pursat Provinces, Cambodia. As the malaria situation in these areas is dynamic, the villages will be identified prior to the start of the trial from analysis of up to date malaria incidence from passive surveillance collected by the Cambodia National Center for Parasitology Entomology and Malaria Control. If there are found to be insufficient villages with malaria cases in Stung Treng Province at the time of trial commencement, we will include additional sites in Pursat Province. MORU has existing study sites and teams in both provinces which will support the running of this trial. The rationale for choosing these areas include high forest cover and ongoing malaria transmission among forest goers.

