6.3. Randomisation and blinding

Participants who fulfil all the inclusion criteria and have none of the exclusion criteria will be randomised 1:1 to one of the two treatment arms according to a randomisation schedule. Randomisation will be in blocks of size that will be determined by the trial statistician and the block

size will not be revealed to the investigating team. Allocation will be done by drawing the next sequential numbered opaque envelope (or other equally reliable randomisation administration procedure), which contains the study number and treatment allocation.

The participants will be assigned a study arm through a computer-generated randomisation schedule. Individual, sealed and sequentially numbered envelopes will be provided for each trial site with one envelope per participant, indicating the treatment allocation.

This is an open-label study so the blinding of investigators and participants is not applicable. However, the randomisation procedure allows for adequate drug allocation concealment before envelopes are opened. All laboratory investigations will be performed without knowledge of the treatment allocation.

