### Table 1. Baseline Characteristics of the Participants

Characteristics	Artemether-Lumefantrine (N=XXX)	Multivitamin (N=XXX)	Total (N=XXX)
Demographics			
Age (years), median (IQR)	XX.X (XX.X - XX.X)	XX.X (XX.X - XX.X)	XX.X (XX.X - XX.X)
Male sex, n (%)	XX (XX.X)	XX (XX.X)	XX (XX.X)
Weight (kg), mean (SD)	XX.X (XX.X)	XX.X (XX.X)	XX.X (XX.X)
Tympanic temperature* (°C), mean (SD)	XX.X (XX.X)	XX.X (XX.X)	XX.X (XX.X)
Nationality, n (%)			
Khmer	XX (XX.X)	XX (XX.X)	XX (XX.X)
Laos	XX (XX.X)	XX (XX.X)	XX (XX.X)
Thai	XX (XX.X)	XX (XX.X)	XX (XX.X)
Others (including English)	XX (XX.X)	XX (XX.X)	XX (XX.X)
Occupation, n (%)			
Farmer	XX (XX.X)	XX (XX.X)	XX (XX.X)
Fishing	XX (XX.X)	XX (XX.X)	XX (XX.X)
Student	XX (XX.X)	XX (XX.X)	XX (XX.X)
Millitary	XX (XX.X)	XX (XX.X)	XX (XX.X)
Housewife	XX (XX.X)	XX (XX.X)	XX (XX.X)
Others	XX (XX.X)	XX (XX.X)	XX (XX.X)
Place of residence, n (%)			
Stung Treng	XX (XX.X)	XX (XX.X)	XX (XX.X)
Siem Pang	XX (XX.X)	XX (XX.X)	XX (XX.X)
Others	XX (XX.X)	XX (XX.X)	XX (XX.X)
Participants with prior malaria episodes , n (%)	XX (XX.X)	XX (XX.X)	XX (XX.X)
Symptoms, n/N (%)			
Headache	XX/XX (XX.X)	XX/XX (XX.X)	XX (XX.X)
Loss of appetite	XX/XX (XX.X)	XX/XX (XX.X)	XX (XX.X)
Dizziness	XX/XX (XX.X)	XX/XX (XX.X)	XX (XX.X)
Joint pain	XX/XX (XX.X)	XX/XX (XX.X)	XX (XX.X)
Abdominal pain	XX/XX (XX.X)	XX/XX (XX.X)	XX (XX.X)
Fatigue	XX/XX (XX.X)	XX/XX (XX.X)	XX (XX.X)
Nausea	XX/XX (XX.X)	XX/XX (XX.X)	XX (XX.X)
Vomiting	XX/XX (XX.X)	XX/XX (XX.X)	XX (XX.X)
Diarrhoea	XX/XX (XX.X)	XX/XX (XX.X)	XX (XX.X)
Itching/ rash	XX/XX (XX.X)	XX/XX (XX.X)	XX (XX.X)

Cough	XX/XX (XX.X)	XX/XX (XX.X)	XX (XX.X)
Antimalarial drug history, n			
(%)			
Drug1	XX (XX.X)	XX (XX.X)	XX (XX.X)
Drug2	XX (XX.X)	XX (XX.X)	XX (XX.X)
Drug3	XX (XX.X)	XX (XX.X)	XX (XX.X)
ect.	XX (XX.X)	XX (XX.X)	XX (XX.X)
Medical history, n (%)			
Disease1	XX (XX.X)	XX (XX.X)	XX (XX.X)
Disease2	XX (XX.X)	XX (XX.X)	XX (XX.X)
Disease3	XX (XX.X)	XX (XX.X)	XX (XX.X)
etc.	XX (XX.X)	XX (XX.X)	XX (XX.X)
Malaria history, n (%)			
Malaria1	XX (XX.X)	XX (XX.X)	XX (XX.X)
Malaria1	XX (XX.X)	XX (XX.X)	XX (XX.X)
Malaria1	XX (XX.X)	XX (XX.X)	XX (XX.X)
etc.	XX (XX.X)	XX (XX.X)	XX (XX.X)
Physical examination, n (%)			
Movement abnormality	XX (XX.X)	XX (XX.X)	XX (XX.X)
Skin abnormality	XX (XX.X)	XX (XX.X)	XX (XX.X)
Eyes abnormality	XX (XX.X)	XX (XX.X)	XX (XX.X)
Breathing abnormality	XX (XX.X)	XX (XX.X)	XX (XX.X)
Speech abnormality	XX (XX.X)	XX (XX.X)	XX (XX.X)
Hearing abnormality	XX (XX.X)	XX (XX.X)	XX (XX.X)

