4.3 ANALYSIS OF PRIMARY OUTCOME

Primary objective:

To compare the efficacy of the ACT artemether-lumefantrine versus a multivitamin preparation as defined by the 28-day PCR parasite positivity rate or incidence of confirmed clinical malaria of any species

Primary endpoints:

Composite endpoint

- 1. 28-day PCR Plasmodium positivity rate of any species or
- 2. Proportion of participants with confirmed clinical malaria of any species reported between day 0 and day 28

The main analysis strategy for the primary outcome will be the intention-to-treat (ITT) principle followed by the per protocol (PP) analysis. Thus, we will first analyse the ITT population in which all participants recruited in the trial will be included in the analysis according to the randomisation arm irrespective of what they actually got. These ITT analyses will be followed by the analysis of the per protocol (PP) population in which, participants who did not adhere to the protocol will be excluded from analysis.

The efficacy of the ACT artemether-lumefantrine versus a multivitamin preparation as defined by the 28-day PCR parasite positivity rate or incidence of confirmed clinical malaria analysis in each arm will be summarised using proportions and the 95% confidence intervals. Crude proportions will be calculated with the exact binomial 95% confidence intervals. The risks differences in efficacy between AL and multivitamin will be reported along with the corresponding 95% confidence intervals. The robust standard error will be used to adjust for intracluster correlation of episodes from the same individual. The mixed effects Poisson/negative binomial regression model will be used to model the adjusted incidence rate ratios (IRR). The mixed effects models will take into account the correlation of multiple episodes from same participant.

Tests of significance will be performed at 5% significance level.

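### Allocation is blocked separately within each trial site, but SAP 4.3 names no site term, so the primary analysis is slightly conservative if risk differs between sites

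*Protocol*

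**What the plan says.** Protocol 6.3 states that eligible participants "will be randomised 1:1 to one of the two treatment arms". On the method it says: "Randomisation will be in blocks of size that will be determined by the trial statistician". On administration it says: "Individual, sealed and sequentially numbered envelopes will be provided for each trial site with one envelope per participant, indicating the treatment allocation". It also allows another equally reliable procedure in place of envelopes. It does not use the word stratified and does not define a trial site.

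On the setting, Protocol 5.1 says: "The study will take place at up to 50 villages in selected malaria endemic districts". It adds: "As the malaria situation in these areas is dynamic, the villages will be identified prior to the start of the trial". The choice rests on recent passive surveillance incidence.

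SAP 4.3 plans a risk difference with robust standard errors for episodes from the same individual, and a mixed-effects Poisson or negative binomial model for adjusted incidence rate ratios (IRRs). On the model it says: "The mixed effects models will take into account the correlation of multiple episodes from same participant". Site, village and province are not named as a stratum, fixed effect or random effect in either analysis, and no covariate is listed behind the word adjusted.

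**The concern.** Blocks run through a separate sequential series at each site keep the arms close to equal within site. Differences in risk between sites then largely cancel out of the treatment comparison. An analysis that leaves site out still counts those differences as noise. Its SE is too large, its interval too wide and its test conservative.

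Two things are at stake. One is a small loss of precision that the design has already paid to avoid. The other is prespecification: because the IRR is called adjusted with no covariates listed, the plan does not settle whether site enters the model, and this is an open-label trial.

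**Working it through.** **Inputs from the documents.** 5% v 3% positivity, 80% power, 5% significance, 1,605 episodes per arm required and 4,400 planned (Protocol 9.1, SAP 2.5); up to 50 villages (Protocol 5.1). This gives 4,400/50 = 88 episodes per village on average.

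**Assumptions.** Between-village variation is not given, so it is shown over a range. Each person contributes one record unless stated otherwise. Site is first taken to mean village, then a larger unit.

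**Step 1: the plan's own figure.** With mean risk 0.04 and difference 0.02:

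n = [1.96·√(2·0.04·0.96) + 0.8416·√(0.05·0.95 + 0.03·0.97)]² / 0.02² = 1,506 per arm.

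The continuity correction, n/4·[1 + √(1 + 4/(n·0.02))]², gives 1,605. The stated figure reproduces exactly (two-sided).

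**Step 2: analytic size of the excess.** Write CV for the coefficient of variation of village risk and p for mean risk. The between-village share of the outcome variance is

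ICC = CV²p² / [p(1−p)] = CV²·p/(1−p).

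If balance is forced within village, the ratio of unadjusted to stratified SE is 1/√(1−ICC). With p = 0.04:

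| CV | ICC | SE ratio |
|---|---|---|
| 0.5 | 0.0104 | 1.005 |
| 1.0 | 0.0417 | 1.022 |
| 1.5 | 0.0938 | 1.051 |
| 2.0 | 0.1667 | 1.095 |

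Simulation at 5% v 3% (50 villages × 88 episodes, blocks of 4, gamma-distributed risk, 4,000 runs) gives 1.005, 1.022, 1.051 and 1.094, and 1.000 when villages do not differ.

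**Step 3: logit-normal village risk, no effect, mean risk 5%, allocation 1:1 within village.**

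| Village logit SD | Excess width of unadjusted SE | Type I error, unadjusted |
|---|---|---|
| 0.5 | about 0% | about 5.0% |
| 1.0 | about 2-3% | about 4.2% |
| 1.5 | about 7% | about 3.5% |

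For example, at SD 1.0 the unadjusted SE is 0.00653 and the stratified SE 0.00635 (ratio 1.028). At SD 1.5 they are 0.00654 and 0.00610 (ratio 1.072). Repeat runs put type I error at 4.0-4.6% for SD 1.0 and 3.3-4.0% for SD 1.5. An empirical SD from 4,000 runs has a relative error of about 1/√8,000 = 1.1%, so single percentage points should not be over-read.

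**Step 4: power at 5% v 3%, 2,200 per arm.** Unadjusted v stratified: 92.6% v 93.2% at SD 1.0 (0.6 points) and 91.1% v 92.4% at SD 1.5 (1.3 points).

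**Step 5: site is a large unit.** With the Step 3 setting but allocation balanced only within two sites, the ratio of unadjusted to true SE is 1.00, 1.00 and 0.99 at SD 0.5, 1.0 and 1.5, and type I error is 5.1%, 4.5% and 4.9%. The excess disappears.

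**Step 6: more than one record per enrolment.** With three monthly rows each and an assumed within-person correlation of 0.2, the village share becomes 3·ICC/(1 + 2·0.2). The SE ratio is then 1.01, 1.05 and 1.12 at CV 0.5, 1.0 and 1.5. This is an upper case, since not every enrolment has three follow-ups.

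All figures are for the risk difference. The IRR model was not simulated.

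**The case against.** The strongest objection is that the size of the effect depends on trial site meaning village, which the documents never say. Several passages suggest something larger. Protocol 5.1 refers to existing study sites and teams in the two provinces, 8.2 to a site investigator, 11.1 to sites with their own internal monitoring, and 16 to sites publishing their own data. Step 5 shows the excess vanishing for two large sites. This stands, and it makes the figures in Step 3 conditional.

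Second, the larger figures need a wide spread. A logit SD of 1.5 puts the central 95% of villages between about 0.1% and 29% risk, and choosing villages on malaria incidence works against the low end. This also stands. At SD 0.5, where villages already range from about 1.7% to 11%, there is no material loss.

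Third, the word adjusted may be meant to include site. It may, but no covariate is listed, so the plan does not commit to it.

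Stronger readings are tempting and are not supported. A reader might infer that omitting site makes the intervals too narrow or inflates type I error. With individual randomisation balanced within site, the direction is the opposite. A reader might also take the missing Pursat row in SAP Table 1 as hiding site differences. That table has a row for other places, Protocol 5.1 makes added Pursat sites depend on finding too few villages with cases in Stung Treng, and stratification gives one pooled effect whatever the table's rows. That is a clerical matter and not part of this point.

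**Conclusion.** The point holds as one of efficiency and specification. Allocation is in effect stratified by site through blocks plus a separate envelope series, and SAP 4.3 does not carry site into either primary analysis.

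If site is village, which is an inference, the SE is about 0%, 2-3% or 7% too wide at an assumed village logit SD of 0.5, 1.0 or 1.5. Type I error is then about 5.0%, 4.2% or 3.5%, and the power cost is about 1 point or less. Repeated rows per enrolment could raise the excess somewhat; a few large sites would bring it close to zero. The effect is small because the outcome is rare. The error is on the conservative side, so validity is not threatened and the sample size need not change. The change is worth making because it costs little and lets the analysis follow the randomisation.

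**What to change.** In SAP 4.3:

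- State what a trial site is, as the unit that held its own envelope series.
- Estimate the primary risk difference stratified by that site, for example with Mantel-Haenszel weights, and keep the person-level robust errors.
- Fix in advance a rule for pooling sparse sites within province. At 88 episodes and 3-5% risk, a village would have about 88·0.03 = 2.6 to 88·0.05 = 4.4 events.
- Include the same site as a term in the Poisson/negative binomial model, list every other covariate behind the adjusted IRR, and name a fallback if the model does not converge.

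Stratify by the actual randomisation unit and nothing finer. A village-level SE that treats the arms as balanced, when balance was forced only within larger sites, removes variance that the design did not remove and can be too small.

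The cost is SAP wording and a few lines of code, with no change to conduct. The downsides are sparse strata and possible non-convergence. The documents do not say that the issuing site is recorded for every enrolment (Protocol 6.3 describes the envelope as holding the study number and allocation), so this should be confirmed first.

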6.4. Blood sampling on study enrolment

On study enrolment, immediately before drug administration, blood will be collected for the following:

- Parasite PCR (Up to 1 ml).
- Dried blood spot for capillary blood level of lumefantrine (200 µl)
- Storage for later identification of other causes of fever (2ml).

6.5. Study drug administration

Overview PAL drug regimens	
ACT arm	Multivitamin arm
Artemether -lumefantrine x 3 days followed by 1 day per week	Multivitamin x 3 days followed by 1 day per week

Participants will be treated with weight-based doses according to the schedule in Appendix 2.

The study drugs will be administered by trained study staff.

If the participant vomits within half an hour after intake of the antimalarial drugs, the dose will be repeated. If vomiting occurs between half and one hour, half of the dose will be repeated. If vomiting occurs more than one hour after drug administration, no repeat dosing will be done. Repeat doses will be recorded on the CRF. If vomiting within 1 hour occurs more than one time, no repeat dosing is allowed. The participant will then be treated at the discretion of the investigator.

The prophylaxis will start with a 3-day course of twice daily AL. This will be followed by 2 doses 8 hours apart on one day per week during the time that the person is travelling in the forest and for 4 weeks after leaving the forest.

6.6. Follow-up

Participants will be asked to return for a follow-up assessment any time from 28 to 35 days after commencing prophylaxis. This will be regardless of the duration of their visit to the forest or the number of times they visited it in that period. At this assessment, they will be interviewed about how long they spent in the forest, where they went, why, who they travelled with and about risk factors for infection. Brief physical examinations, vital sign and symptom questionnaire will be performed. They will also be asked to report any diagnostic tests and/or treatment for malaria during the preceding 28-35 days.

Blood sampling at follow-up

At each follow-up visit, the following blood will be taken:

All individuals:

- Parasite PCR (Up to 1 ml).

- Dried blood spot for lumefantrine level (0.2 ml)

In those with confirmed clinical malaria at any time point between enrolment and follow-up:

- Dry blood blots (0.4 ml, 3 spots) collected on filter papers for:
 - o Parasite DNA genotyping for genetic markers of antimalarial resistance.
 - o Parasite whole genome sequencing and barcoding to identify geographical origin of parasites and compare genotypes to identify persistent infections.

In individuals who are planning to return again to the forest within the following 28 days after the follow up visit, they will be asked to continue their weekly prophylaxis according to the original treatment allocation on enrolment. They will then be asked to return for a second follow-up visit a further 28 to 35 days later when the above procedure will be repeated. This will be repeated one more time. If the person cannot be followed up within the scheduled period, e.g. because they do not return from the forest in time, then they will be followed up at the first opportunity and this will be recorded in the CRF.

Thus individuals may take prophylaxis continuously for a maximum of 3 periods of 28-35 days in the forest plus 4 weeks after returning totaling 112 days. The choice of study medication for each individual will follow the initial assignment on enrolment throughout the follow-up period.

In those who do not declare an intention to return to the forest within 28 days at any follow-up visit, no further follow-up visits will be offered at that time but they will be asked to complete 4 weeks of prophylaxis following their last day in the forest as post-exposure prophylaxis.

Individuals who have been enrolled in the study may be enrolled into the study up to two more times during the 12 months study period only if a minimum period of 28 days (4 weeks) has elapsed following their last dose of prophylaxis. Thus they can be enrolled in the study a maximum of three times. If an individual is enrolled again in this way, they will be re-randomised following the same procedure as enrolment.

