5.4 Primary and secondary endpoints

5.4.1. Co-primary Endpoints

1. 28-day PCR positivity rate of *Plasmodium* infections of any species.
2. Proportion of participants with confirmed clinical malaria of any species reported between day 0 and day 28

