6.6.1 Time windows

The time-window for the follow-up visits is 28-35 days. If a participant does not attend, the study team will try to locate the participant and bring them to the village.

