6.6.2 Additional visits

Participants presenting to the village malaria worker, mobile malaria worker or clinic with a fever or other symptoms at any time after enrolment that is not a scheduled study follow-up visit will be assessed and treated by the healthcare workers in the local healthcare system as per routine clinical practice in Cambodia.

On enrolment, participants will be encouraged to attend a village malaria worker or government clinic for the assessment of fever or other symptoms and to report this to the study team as soon as possible after the symptoms occur. Information on these healthcare encounters including malaria test result and treatment will be recorded in the study CRF.

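### The follow-up question on malaria looks back 28-35 days, so at a first visit after day 35 it no longer reaches the start of the day 0-28 endpoint period

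*Protocol*

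**What the plan says.** Protocol 5.4.1 makes clinical malaria one of two co-primary endpoints: "Proportion of participants with confirmed clinical malaria of any species reported between day 0 and day 28". SAP 4.3 treats it as one component of a composite primary endpoint, and SAP 2.2 applies it at each of the three monthly follow-ups. Protocol 3.3 states the intended coverage: "Episodes of confirmed clinical malaria among study participants at any time point between enrolment and follow-up will also be recorded".

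Protocol 6.6 sets the visit timing: "Participants will be asked to return for a follow-up assessment any time from 28 to 35 days after commencing prophylaxis". Section 6.6.1 repeats it: "The time-window for the follow-up visits is 28-35 days". The interview item on malaria is this: "They will also be asked to report any diagnostic tests and/or treatment for malaria during the preceding 28-35 days".

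Section 6.6 also provides for people who cannot be seen on schedule, for example "because they do not return from the forest in time, then they will be followed up at the first opportunity". It gives no latest day for such a visit and does not lengthen the look-back.

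Other sections also bear on finding episodes:

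- 6.6.2 encourages participants who seek care for fever or other symptoms "to report this to the study team as soon as possible after the symptoms occur", and the test result and treatment go into the CRF.
- 6.11 links participants who have confirmed malaria during follow-up to their case records, in order to quantify incidence by arm.
- 6.6.3 takes blood from confirmed cases from enrolment until one month after the last visit.
- 6.6.1 has the team try to find non-attenders.

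The SAP does not say which source defines a clinical episode, or how visits after day 35 are handled.

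**The concern.** The look-back is fixed while the visit day is open-ended. For an on-schedule visit the two agree. Once the visit slips past day 35, the days that drop out of the question are the earliest days of the endpoint period.

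Lateness is not random with respect to risk. The protocol's own example of a late attender is someone still in the forest, where exposure is highest. An episode that was diagnosed and treated early may no longer be PCR-positive at a late visit. If it was not reported at the time, both parts of the primary endpoint could miss it. At stake is under-ascertainment of clinical malaria among the participants with the longest exposure.

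**Working it through.** **Inputs.** Endpoint period: day 0 to day 28 (Protocol 5.4.1, SAP 4.3). Look-back: at most 35 days (Protocol 6.6). First visit: day 28-35, or later without limit (6.6). T is the day of the first visit, counted from the start of prophylaxis.

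**Days of the endpoint period not asked about.** The question reaches back to day T − 35, so

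unasked days = min(28, max(0, T − 35)).

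| First visit on day | Unasked days | Share of the 28 days |
|---|---|---|
| 35 | 0 | 0% |
| 38 | 3 | 11% |
| 42 | 7 | 25% |
| 49 | 14 | 50% |
| 56 | 21 | 75% |
| 63 or later | 28 | 100% |

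For a second or third visit that falls G days after the previous one, the first max(0, G − 35) days of that interval are not asked about.

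**Set against the stated intent.** Protocol 3.3 promises coverage from enrolment to follow-up. For any first visit after day 35, the question as written cannot deliver that alone. Section 3.3 also times follow-up at 28 days, plus or minus 7, after return from the forest, which differs from 6.6. If a site worked to 3.3, and a participant left on day 0 and stayed 10 days (9.1 assumes at least 10 risk days per episode), the visit would fall on day 10 + 21 = 31 to day 10 + 35 = 45. Section 6.6 is the operative procedure, but this is a further reason to tie the look-back to enrolment.

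**Person-time, for illustration.** The share of late visits is not in the documents. If a fraction f attend on a day that leaves a share m unasked, the unasked part of all day 0-28 person-time is f × m. With an assumed 10% attending on day 49, this is 0.10 × 0.50 = 5%. With f between 5% and 20% it is 2.5% to 10%.

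**The plan's own figure.** The only formal calculation is 1,605 episodes per arm for 5% versus 3% P. falciparum PCR positivity, at 80% power and 5% significance. The two-sided comparison of two proportions gives 1,506 without and 1,605 with continuity correction, so the figure reproduces. It does not rest on the interview and would not change. At 2,200 per arm, power is 92% (normal approximation, no continuity correction, no allowance for losses or repeated episodes).

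**A stress test of power.** Suppose that the interview were the only source, that loss were equal in both arms, that risk were even over time and the same in late attenders, and that 5% and 3% stood in for clinical-malaria rates, which the documents do not give. Both rates are then multiplied by k = 1 − f × m.

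- f = 5%, m = 25%: k = 0.9875; 4.94% versus 2.96%; difference 1.98 points; power 92%.
- f = 10%, m = 50%: k = 0.95; 4.75% versus 2.85%; difference 1.90 points; power 91%.
- f = 30%, m = 100%: k = 0.70; 3.5% versus 2.1%; difference 1.4 points; power 80%.

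The risk ratio stays at 0.6 throughout. The sole-source assumption overstates the loss. The equal-risk assumption would understate it if late attenders are at higher risk.

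**The case against.** The best reply is that the phrase is loose wording. It repeats the visit window, so its natural sense is the time since prophylaxis began or since the previous visit: 28 days at a day-28 visit, 35 at a day-35 visit. This stands for on-schedule visits. A reader might take the look-back as a flat 28 days and conclude that even a day-35 visit loses a week, but that reading is strained and nothing here relies on it. The reply does not settle visits after day 35, where the text gives a number that is too short.

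The second reply is that the interview is not the only route. A reader might infer that prompt self-report is all that remains between visits, and section 6.11 contradicts that. Sections 6.6 and 6.6.3 and Appendix 1 also frame confirmed malaria as running from enrolment, and 6.6.1 limits lateness through active tracing. Moreover, a confirmed episode implies contact with someone who tested, so the participant was not wholly out of reach. All this stands as partial cover, with limits. Section 6.11 concerns participants who have had an episode and does not say that records are searched for everyone, so it may only verify cases already known. Sampling of confirmed cases likewise requires the case to be known. Section 6.6.2 depends on the participant then telling the study team.

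**Conclusion.** The mismatch is real but limited. Under the literal wording, a first visit after day 35, or a later visit more than 35 days after the previous one, leaves the start of the interval outside the only systematic malaria question put to every attender. This conflicts with section 3.3 and with the day 0-28 endpoint. Some early treated episodes in the longest-exposed participants could be missed.

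A reader might go further and infer that such episodes are lost, that the participants are scored malaria-free, or that the comparison between arms is biased. The documents do not support this. Other routes may pick the episodes up, no section says how unasked days are scored, and neither the share of late visits nor any difference in lateness between arms is given. Unequal loss is conceivable in an open-label trial, but nothing shows it. The power figures depend on assumed late shares and on the interview as sole source, so they are not an estimate. No figure in the protocol or SAP is wrong because of this. Severity is minor to moderate.

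**What to change.** In Protocol 6.6 and on the follow-up CRF, replace the reference to the preceding 28-35 days with *since enrolment* at the first visit and *since the last study visit* at later visits. Record the date of each test and treatment, so that the SAP 4.3 analysis can assign every episode to its window whatever the visit date. The number of unasked days then becomes zero for any visit day.

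The cost is one sentence and one CRF item with dates, with no extra visit or sample and no change to the sample size. The small downside is a longer recall period for late attenders.
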